4.2.2.1.1 Subgroup analyses

Subgroup analyses will be conducted, summarising ORR in the treatment groups in the following subgroups of the FAS:

- Prior lines of therapy (osimertinib monotherapy as first line versus \geq second line)
- FISH allocation status (amplified versus polysomy, or missing).

The subgroups for prior lines of therapy will be determined by the values entered into the IWRS at randomisation, even if it is subsequently discovered that these values were incorrect.

All patients randomised in the study will be MET amplified (FISH+). The FISH allocation status of amplification is considered a ratio of 'Mean MET/CEP7 RATIO' ≥ 2 , and polysomy where this ratio < 2 . If the ratio variable is missing, patients will be presented in a missing category.

The purpose of the subgroup analyses is to assess the consistency of treatment effect across expected prognostic and/or predictive factors. These subgroup analyses will be repeated for the FISH10+ biomarker group and for the **CCI** biomarker group.

4.2.3 Secondary Efficacy Endpoints

4.2.3.1 Progression free survival (PFS)

The PFS will be based on the site investigator RECIST data, and using all scans regardless of whether they were scheduled or not. The PFS will be summarised in both treatment arms.

If there are at least 20 events, the effect of treatment will be estimated by the hazard ratio (HR) (an HR less than 1 will favour savolitinib plus osimertinib) together with its corresponding 95% CI for the FAS. The HR and its CI will be estimated from a stratified Cox Proportional Hazards model (with ties = Efron and baseline stratification), adjusting for the number of prior lines of therapy (osimertinib monotherapy as first line or \geq second line [which includes patients who received osimertinib monotherapy before or after chemotherapy]), and the CI calculated using a profile likelihood approach.

Kaplan-Meier plots of PFS will be presented by treatment arm. Summaries of the number and percentage of patients experiencing a PFS event, and the type of event (RECIST 1.1 progression or death) will be provided along with summaries of PFS (n, events, medians, quartiles, proportion progression free at 3, 6, 9, and 12 months and corresponding 95% CIs) by treatment group. The number and percentage of patients censored in the analysis as well as by reason for censoring will be provided for each treatment group.

This analysis of PFS will be repeated for second line patients (i.e. patients with one prior line of therapy before the study treatment).

These analyses will also be produced for PFS per BICR. If there is an important discrepancy between the primary analysis using the site investigator data and this sensitivity analysis using BICR data then the proportion of patients with site but no central confirmation of progression will be summarised; such patients have the potential to induce bias in the central review due to informative censoring. Disagreements between investigator and central reviews of RECIST progression will be presented for each treatment group.

The effect of treatment will be estimated by the HR for second line patients and per BICR only if there are at least 20 events within those analysis sets.

The treatment status at progression of patients at the time of analysis will be summarised based upon the FAS. This will include the number (%) of patients who were on treatment at the time of progression, the number (%) of patients who discontinued study treatment prior to progression, the number (%) of patients who have not progressed and were on treatment or discontinued treatment. This will also provide distribution of number of days prior to progression for the patients who have discontinued treatment.

4.2.3.2 Duration of response (DoR)

Descriptive data (n, number of responses that have progressed, median, quartile, minimum and maximum DoR) will be provided by treatment group for the duration of response in responding patients, including the associated Kaplan-Meier curves (without any formal comparison or p-value attached). These analyses and plots will be repeated for second line patients.

Descriptive summaries for the DoR will be based upon the FAS.

4.2.3.3 Overall survival (OS)

Overall survival will be analysed as described for the investigator-assessed PFS endpoint in Section 4.2.3.1, with the exception that the analyses will not be repeated in second line patients.

Summaries of OS by treatment arm (n, events, medians, quartiles, proportion alive at 3, 6, 9 and 12 months and corresponding 95% CIs) based upon the FAS and a Kaplan-Meier plot will be provided.

In addition, duration of follow-up will be summarised using medians in all patients based upon the FAS, calculated as the time from randomisation to the date of death (i.e. overall survival) or

to the date of censoring (date last known to be alive) for censored patients, regardless of treatment arm.

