Under CSP V3.0, as a result of AstraZeneca's decision to terminate study recruitment early, the planned interim futility analysis and primary analysis will not be performed, and there will be no requirement for data review by the IDMC. Alternatively, an initial data cut-off (DCO) will occur following the early termination of study recruitment to allow an early review of the data by AstraZeneca. The study will be unblinded after completion of data cleaning activities on the initial DCO data, and patients on savolitinib monotherapy (savolitinib plus placebo) will be given the opportunity to cross-over to the savolitinib plus osimertinib arm after approval by AstraZeneca.

If it is decided that a patient will switch to savolitinib plus osimertinib before final database lock, then they will follow the scheduled procedures described in CSP Table 2. Patients may otherwise choose to remain on savolitinib monotherapy (as long as, in the opinion of the investigator, they are still receiving clinical benefit and have not reported PD). All patients will be followed until the final DCO for the final analysis, which will occur after all randomised patients have had a 9-month follow-up. CCI

For an overview of the study design see [Figure 1](#).

Figure 1 Study Design

EGFRm+ = Epidermal growth factor receptor mutation positive; MET = Hepatocyte growth factor receptor; NSCLC = Non-small cell lung cancer.

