1.3 Number of patients

Prior to CSP V3.0, the treatment of approximately 56 patients (28 per arm) with EGFRm+ and MET amplified locally advanced or metastatic NSCLC who have progressed following treatment with osimertinib was considered adequate for this study. CCI

At least half of the patients planned to be randomised into the study will be second-line patients who were treated with osimertinib as first-line therapy.

Under CSP V3.0, the planned number of randomised patients will not be met. This is a result of the decision by AstraZeneca to terminate study recruitment early.

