3.2.4 Overall survival (OS)

Overall survival is defined as the time from the date of randomisation until death due to any cause regardless of whether the patient withdraws from randomised therapy or receives another anti-cancer therapy (i.e. date of death or censoring – date of randomisation + 1). Any patient not known to have died at the time of analysis will be censored based on the last recorded date on which the patient was known to be alive (SUR_DAT, recorded within the SURVIVE module of the eCRF).

Note: Survival calls will be made in the week following the date of data cut-off (DCO) for the analysis, and if patients are confirmed to be alive or if the death date is post the DCO date these patients will be censored at the date of DCO. The status of ongoing, withdrawn (from the study) and “lost to follow-up” patients at the time of the final OS analysis should be obtained by the site personnel by checking the patient’s notes, hospital records, contacting the patient’s general practitioner and checking publicly-available death registries. In the event that the patient has actively withdrawn consent to the processing of their personal data, the vital status of the patient can be obtained by site personnel from publicly available resources where it is possible to do so under applicable local laws.

Note: For any OS analysis performed prior to the final OS analysis, in the absence of survival calls being made, it may be necessary to use all relevant CRF fields to determine the last recorded date on which the patient was known to be alive for those patients still on treatment (since the SURVIVE module is only completed for patients off treatment if a survival sweep is not performed). The last date for each individual patient is defined as the latest among the following dates recorded on the CRFs:

- AE start and stop dates
- Admission and discharge dates of hospitalization
- Study treatment date
- End of treatment date
- Laboratory test dates

- Date of vital signs
- Disease assessment dates on RECIST CRF
- Start and stop dates of alternative anticancer treatment
- Date last known alive on survival status CRF
- End of study date.

If a patient is known to have died where only a partial death date is available, then the date of death will be imputed as the latest of the last date known to be alive + 1 from the database and the death date using the available information provided:

- a. For Missing day only – using the 1st of the month

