4.2.4 Data cut-offs

The data cut-off for futility analysis was planned to take place after 20 patients overall (10 per arm) have had the opportunity to be treated for 2 RECIST post-baseline scans (12 weeks). In order to ensure that 10 patients in the savolitinib plus placebo group have been randomised for inclusion into the futility analysis set, the IWRS was to be used to determine when 22 patients have been randomised into the study.

The data cut-off for primary analysis was planned to take place 6 months after last subject in (LSI). The data cut-off for final analysis was planned to take place at the earlier of 18 months after LSI or when 70% of patients have progressed or died.

Under CSP v3.0, an initial DCO will occur to allow an early review of data by AstraZeneca. A final DCO will occur 9 months after the last patient has been randomised, after which the final analysis will be performed. CCI These changes are a result of the decision by AstraZeneca to terminate study recruitment early.

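### The planned median duration of follow-up is the median of observed OS time, so it falls as mortality rises and understates potential follow-up

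*SAP*

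**What the plan says.** SAP section 4.2.3.3 has duration of follow-up "summarised using medians in all patients based upon the FAS, calculated as the time from randomisation to the date of death (i.e. overall survival") for patients who die. For the others it runs "to the date of censoring (date last known to be alive) for censored patients, regardless of treatment arm". The text itself equates the first part with overall survival.

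Section 3.2.4 defines OS time as "date of death or censoring – date of randomisation + 1". It adds that, after the survival calls, "if patients are confirmed to be alive or if the death date is post the DCO date these patients will be censored at the date", that is, at the cut-off. The follow-up variable and the OS variable are therefore the same quantity.

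Elsewhere the SAP uses follow-up to mean time up to the cut-off. Section 1.2 places the final cut-off at a point "which will occur after all randomised patients have had a 9-month follow-up". Section 4.2.4 gives the same timing: "A final DCO will occur 9 months after the last patient has been randomised, after which the final analysis will be performed".

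The SAP specifies no reverse Kaplan-Meier summary, no median restricted to censored patients and no follow-up figure by arm. It does not say whether the medians are simple or Kaplan-Meier.

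**The concern.** A follow-up summary tells the reader how long patients could have been observed, so that the survival results can be read with the right caution. Under section 4.2.3.3 every earlier death shortens the reported figure. Two trials with the same accrual and the same cut-off would report different follow-up if their mortality differed, and the one with more deaths, and so more OS information, would look less mature.

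This matters here because recruitment stopped early and the guaranteed window is 9 months, while section 4.2.3.3 also plans proportions alive at 12 months. How well those 12-month estimates are supported depends on how many patients were randomised at least 12 months before the cut-off. The planned figure does not show that. It could even come out below 9 months in a trial that met its own rule for the final cut-off.

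**Working it through.** The SAP states no follow-up figure, so there is none to reproduce. The check compares what the definition returns with potential follow-up.

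**Inputs from the SAP.** The earliest administrative censoring is 9 months after randomisation (sections 1.2 and 4.2.4). Patients confirmed alive are censored at the cut-off (section 3.2.4). The number randomised is not given; section 1.3 says only "Under CSP V3.0, the planned number of randomised patients will not be met", the plan having been 56.

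**Assumptions not in the SAP.** Uniform accrual over A months, exponential OS with median m, and no loss to follow-up before the cut-off.

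**Formulas.** Potential follow-up C is uniform on 9 to 9 + A months, so its median is 9 + A/2. The observed time is min(T, C), where T is survival time. Its simple median is the t that solves

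2^(−t/m) × P(C > t) = 0.5,

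where P(C > t) = 1 for t ≤ 9 and (9 + A − t)/A for t between 9 and 9 + A.

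Worked case, A = 12 and m = 12, at t = 10.19: 2^(−10.19/12) = 0.555, (21 − 10.19)/12 = 0.901, and the product is 0.50. The plan's median is 10.2 months; potential follow-up is 9 + 6 = 15.0 months; the shortfall is 4.8 months.

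**Results: median under the plan's definition, in months.**

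| Accrual A | Potential median | m = 6 | m = 9 | m = 12 | m = 18 | m = 24 | m = 36 |
|---|---|---|---|---|---|---|---|
| 6 | 12.0 | 6.0 | 9.0 | 9.7 | 10.5 | 10.9 | 11.3 |
| 12 | 15.0 | 6.0 | 9.0 | 10.2 | 11.6 | 12.4 | 13.3 |
| 18 | 18.0 | 6.0 | 9.0 | 10.5 | 12.5 | 13.7 | 15.0 |
| 24 | 21.0 | 6.0 | 9.0 | 10.7 | 13.1 | 14.7 | 16.5 |

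The smallest shortfall is 12.0 − 11.27 = 0.7 months (A = 6, m = 36). The largest is 21.0 − 6.0 = 15.0 months (A = 24, m = 6).

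**What the figure is.** If at least half of the patients die before censoring begins at 9 months (m ≤ 9 here), it equals median OS. Otherwise it mixes death and censoring times and lies below both median OS and potential follow-up. For example, A = 24 and m = 18 gives 13.1, against 18 and 21.0.

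**Small samples.** With an assumed 30 patients, A = 12 and 3,000 simulated trials, the plan's simple median fell below 9 months in about 53% of trials when m = 9 and 17% when m = 12. The reverse Kaplan-Meier median averaged 15.0 to 15.1 months for m from 9 to 24, against a potential 15.0.

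**If the medians are Kaplan-Meier.** With death as the event, the result is pooled median OS. That is a survival result, and it still does not describe follow-up.

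**The case against.** The strongest reply is that this is a descriptive line with an explicit definition. A reader of the SAP can see what is computed, and it enters no estimate, interval, test or decision. That is correct and limits the weight of the point. It does not help a reader of the study report who sees a median follow-up without the definition.

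Four stronger readings are tempting, and the SAP does not support them:

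- *The figure understates the follow-up actually delivered.* For a patient who dies, time to death is all the OS follow-up there can be. What is understated is potential follow-up.
- *The figure simply measures survival once more than half have died.* With A = 24 and m = 18, the proportion dying before the cut-off is 1 − (2^(−9/18) − 2^(−33/18))/(24 × ln 2/18) = 54%, yet the plan's median is 13.1 and not 18. It also moves with accrual: 11.6, 12.5 and 13.1 for A = 12, 18 and 24 at m = 18.
- *Pooling hides differences between arms in loss to follow-up.* Section 4.2.3.3 analyses OS as section 4.2.3.1 does PFS, and that section gives the number censored and the reasons for each treatment group.
- *The figure misleads on PFS maturity.* PFS is censored at the last evaluable tumour assessment (section 3.2.2), so no follow-up figure based on OS, reverse Kaplan-Meier included, measures it.

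It is also fair that the size of the effect is hypothetical, since accrual, survival and sample size are all assumed.

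**Conclusion.** The point holds as a limited one. The quantity that section 4.2.3.3 calls duration of follow-up is observed OS time, and its median is a downward-biased measure of potential follow-up. The direction follows from the definition, because observed time can never exceed potential time. The size does not: 0.7 to 15 months over the assumed grid, with no early loss to follow-up, and nothing in the SAP narrows that range. If half of the patients die within 9 months, the figure drops below the 9-month minimum of the design. The consequence is confined to how mature the OS results appear, chiefly the 12-month proportions. No treatment estimate or comparison changes. The change is worth making because a better measure costs almost nothing and alters a number that will be reported.

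**What to change.** In section 4.2.3.3, define duration of follow-up by reverse Kaplan-Meier on the FAS: censoring at the cut-off or at the date last known alive counts as the event, and deaths are censored at the date of death. Report the median and quartiles by treatment arm and overall. If the present figure is kept, label it observed time on study and state whether its median is simple or Kaplan-Meier.

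The cost is a short wording change and one additional Kaplan-Meier run on the existing OS variables with the event indicator reversed. No new data are needed.

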4.2.3.4 Change in TL tumour size

The absolute values, absolute change in TL tumour size from baseline and percentage change in TL tumour size from baseline will be summarised using descriptive statistics and presented at each timepoint and by randomised treatment group, based upon the FAS.

The best change in TL tumour size from baseline (where best change in TL size is the maximum reduction from baseline or the minimum increase from baseline in the absence of a reduction) will also be summarised and presented by randomised treatment group. The number and percentage of patients in each treatment group whose best percentage change data is imputed (detailed in Section 3.2.6) will also be presented.

The percentage change in week 12 TL tumour size from baseline will also be summarised and presented by randomised treatment group. The number and percentage of patients in each treatment group whose week 12 data is imputed will also be presented.

Tumour size will also be presented graphically using waterfall plots for each treatment group, to present each patient's week 12 percentage change in TL tumour size as a separate bar, with the bars ordered from the largest increase to the largest decrease. Reference lines at the -30% and +20% change in TL tumour size level will be added to the plots, which correspond with the definition of 'partial response' and 'progressive disease' respectively. All progressions will be marked with a '●' or designated with patterns or colours for ORR categories. The scale in these plots will be fixed to be from -100 to 100 to avoid presenting extreme values. Values that are capped as a result of this restriction to the scale will be marked with '#'. Values will be ordered in descending order, with the imputations due to death appearing first, followed by a gap, followed by all other patients. Imputed values will be clearly marked with '*' and patients with imputation where there is a death or evidence of progression will have different shading to each other and the other patients to make it clear that these are different. These plots will be repeated for second line patients and for \geq third line patients.

Additionally, 'spider' plots will be produced for each treatment group. These will depict each patient's actual change and percentage change from baseline in TL tumour size as a line over time, and progression due to non-target and/or new lesions will be indicated. These plots will be repeated for second line patients and for \geq third line patients.

4.2.4 Data cut-offs

The data cut-off for futility analysis was planned to take place after 20 patients overall (10 per arm) have had the opportunity to be treated for 2 RECIST post-baseline scans (12 weeks). In order to ensure that 10 patients in the savolitinib plus placebo group have been randomised for inclusion into the futility analysis set, the IWRS was to be used to determine when 22 patients have been randomised into the study.

The data cut-off for primary analysis was planned to take place 6 months after last subject in (LSI). The data cut-off for final analysis was planned to take place at the earlier of 18 months after LSI or when 70% of patients have progressed or died.

Under CSP v3.0, an initial DCO will occur to allow an early review of data by AstraZeneca. A final DCO will occur 9 months after the last patient has been randomised, after which the final analysis will be performed. CCI These changes are a result of the decision by AstraZeneca to terminate study recruitment early.

4.2.5 Safety

4.2.5.1 General considerations for safety assessments

Time windows will be defined for any presentations that summarise values by visit. The following conventions will apply:

- The time windows will be exhaustive so that data recorded at any time point has the potential to be summarised. Inclusion within the time window will be based on the actual date and not the intended date of the visit.
- All unscheduled visit data have the potential to be included in the summaries.
- The window for the visits following baseline will be constructed in such a way that the upper limit of the interval falls halfway between the two visits (the lower limit of the first post-baseline visit will be Day 2). If an even number of days exists between two consecutive visits, then the upper limit will be taken as the midpoint value minus 1 day. For example, the visit windows for vital signs data are:
 - Day 8, visit window 2 – 11
 - Day 15, visit window 12 – 18
 - Day 22, visit window 19 – 25
 - Day 29, visit window 26 – 43
 - Day 57, visit window 44 – 71
 - Day 85, visit window 72 – 99
 - Day 113, visit window 100 – 127.
- For summaries showing the maximum or minimum values, the maximum/minimum value recorded on treatment will be used (regardless of where it falls in an interval).
- Listings should display all values contributing to a time point for a patient.
- For visit based summaries, if there is more than one value per patient within a time window then the closest value to the scheduled visit date will be summarised, or the earlier, in the event the values are equidistant from the nominal visit date. The listings will highlight the value for the patient that contributed to the summary table, wherever feasible. Note: in summaries of extreme values all post-baseline values

collected are used including those collected at unscheduled visits regardless of whether or not the value is closest to the scheduled visit date.

- Baseline for safety assessments will generally be the last value obtained prior to the first dose of study medication). Alternatively, if two visits are equally eligible to assess patient status at baseline (e.g., screening and baseline assessments both on the same date prior to first dose with no washout or other intervention in the screening period), the average can be taken as a baseline value. For non-numeric laboratory tests (i.e. some of the urinalysis parameters) where taking an average is not possible then the best value would be taken as baseline as this is the most conservative. In the scenario where there are two assessments on day 1, one with time recorded and the other without time recorded, the one with time recorded would be selected as baseline. Where safety data are summarised over time, study day will be calculated in relation to date of first treatment.
- Per Section 9.4.3 of the CSP, adverse events occurring in the savolitinib in combination with placebo group will be split into two presentations based on whether they occurred before or after cross-over.

Missing safety data will generally not be imputed. However, safety assessment values of the form of “< x” (i.e. below the lower limit of quantification) or > x (i.e. above the upper limit of quantification) will be imputed as “x” in the calculation of summary statistics but displayed as “< x” or “> x” in the listings. Additionally, adverse events that have missing causality (after data querying) will be assumed to be related to study drug.

Furthermore:

- For missing diagnostic dates, if day and/or month are missing, use 01 and/or Jan. If year is missing, put the complete date to missing.
- For missing AE start dates, the following will be applied:
 - a. Missing day: impute the 1st of the month unless month is the same as month of the first dose of study drug then impute first dose date
 - b. Missing day and month: impute 1st January unless year is the same as first dose date then impute first dose date
 - c. Completely missing: impute first dose date unless the end date suggests it could have started prior to this in which case impute the 1st January of the same year as the end date

When imputing a start date ensure that the new imputed date is sensible e.g. is prior to the end date of the AE.

- For missing AE end dates, the following will be applied:

- a. Missing day: impute the last day of the month unless month is the same as month of the last dose of study drug then impute last dose date.
- b. Missing day and month: impute 31st December unless year is the same as last dose date then impute last dose date.

Flags will be retained in the database indicating where any programmatic imputation has been applied, and in such cases, any durations would not be calculated.

- If a patient is known to have died where only a partial death date is available, then the date of death will be imputed as the latest of the last date known to be alive + 1 from the database and the death date using the available information provided:
 - c. For Missing day only: using the 1st of the month
 - d. For Missing day and Month: using the 1st of January

With the exception of exposure data, safety data will not be summarised by biomarker group.

